**Visit 5- Follow-up Assessment Visit (3-months post-intervention):**

All participants recruited within first eight months of recruitment will be invited to return for a 3-month follow-up visit. Outcome assessments and procedure followed in Visits 1 and 4 will be repeated including questionnaires, treadmill protocol, blood sample collection and fitting of activPAL. The treadmill test will be by the investigators who are blinded to the participants group allocation. Participants will be given a prepaid envelope to return activPAL. We shall allow assessment visit window of  $\pm$  2 weeks.

Follow-up Assessment Visit (70 mins)	Time (mins)	Responsible

Complete questionnaires:
 
 
1. Generic quality of life questionnaire (SF-36)
 
2. Intermittent Claudication Questionnaire (ICQ)
 
3. Visual Analogue Scale (VAS)
 
4. Geriatric Depression Scale (Short Form) (GDS-SF)
 
5. Pain Self-Efficacy Questionnaire (PSEQ)
 
6. Illness Perception Questionnaire (IPQ)
 
 
If participant is exiting the study at this point:
 
 
7. TENS feedback questionnaire
 
	20	UA/JB
Treadmill protocol • MPQ (5 minutes post-treadmill protocol)	20	
Fitting of ActivPAL to participants and instruction for use	20	
Taking of blood sample	10	

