### **8.7 Sample size**

For the primary outcome measure, at 80% power and a two-tailed 5% significance level, 16 participants per group will allow detection of an effect size of 1.0 standard deviations of ACD in active TENS group compared to placebo control. Attrition rates in our previous pilot studies ranged from 7.1% to 10% . We will recruit 20 participants in each group, allowing for 20% attrition, and therefore aim to recruit 80 patients. If this effect size were applied to our separate pilot studies, this would provide the ability to detect a change of 169m (TENS) or 322m (SEDRIC) in our primary outcome measure of ACD. Indeed, in these studies, a sample size of 20 per group (TENS) and 14 per intervention group (SEDRIC) was sufficient to detect a significant difference in this outcome measure.

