The superiority comparison will be implemented to compare change in physical activity and PROMs between treatment groups (PE+TENS, PE+Placebo TENS, TENS) versus Placebo TENS. Also superiority comparison will be implemented for within treatment groups from baseline. A non-superiority comparison shall be made between the PE+TENS group versus each of the PE+Placebo TENS, TENS groups. The feasibility, acceptability (the recruitment, retention, outcome completion, intervention uptake and attrition rates, and patient tens feedback) and adverse events data will be summarised by randomised group and overall using descriptive statistics. No formal statistical tests comparing the randomised groups will be pre-specified. Framework analysis will be implemented for the qualitative focus group data.

Statistical analysis and stopping guidance

Interim analysis will not be conducted, and the study will stop at last patient last study visit. All outcomes will be analysed collectively at the end of the study. P-value will be set at $p < 0.05$.

Timing of outcome assessments

Physical activity and PROMs outcomes will be assessed at baseline, end of six weeks intervention (up to 2 weeks window), and 3 months post-randomisation (up to 2 weeks window). The recruitment, retention, outcome completion, intervention uptake and attrition rates will be assessed at the end of the study. Blinding and patients acceptability of TENS and

ease of use will be assessed at the point of patient exit from the study. Further assessment regarding patients' qualitative experience of intervention will be done at 3 months post-randomisation (up to 2 weeks window).

SECTION 4: STATISTICAL PRINCIPLES

Level of confidence interval and p-values

Analysis will be conducted at 95% CI, and 0.05 level of significance.

Adherence and Protocol Deviations:

Patient adherence to the intervention will be defined, as applicable, by patients attendance at the education session, and answering to at least one of the 2-weekly phone calls, and/or using TENS at least 30 mins per day 3x/wkly for at least 50% of the 6 weeks of intervention. Specifically, the TENS log (questionnaire) as well as inbuilt record of TENS device usage will both be used to analyse patients utilisation of TENS. Researcher adherence to intervention protocol will be defined as implementation of intervention and outcome assessment according to the approved study protocol.

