Measure participant's retention throughout the trial and reasons for withdrawal
Monitor, record, manage and follow-up defined adverse events in all groups
Measure uptake of intervention (log of TENS use and attendance at education) and acceptability of these interventions via a questionnaire
Measure blinding fidelity via TENS feedback questionnaire
Outcome completion rate – number of day activPAL is worn at each outcome time point.

Efficacy outcomes

Measurement will be obtained at baseline, following six weeks intervention and at 3 months follow up

Primary efficacy outcomes

Treadmill assessed Absolute Claudication Distance (ACD) (cm).

Secondary efficacy outcomes will include:

Physical activity capacity secondary outcomes

Treadmill assessed Initial Claudication Distance (ICD), assessed by a treadmill exercise using the Gardner treadmill protocol.¹⁹ Measurement will be obtained at baseline, following six weeks intervention and at 3 months follow.

Daily physical activity. We shall specify 3 days activPAL data at each measure as minimum for including patient activPAL data in the efficacy analysis. However, activPAL were time (number of day worn) will be also be reported as part of the feasibility analysis. For secondary efficacy analysis, activPAL data outcomes: total number of **i**) steps; **ii**) upright events; **iii**) walking events; **iv**) Event-based claudication index (ratio of walking events to upright events) participants undertake in a day.²⁰

PROM secondary outcomes

Disease specific quality of life will be as assessed using the Intermittent Claudication Questionnaire (ICQ).

Generic quality of life via the SF-36;

Pain quality will be recorded using the McGill Pain Questionnaire (MPQ) 5 minutes after every treadmill test.

Average Pain intensity in the past 7 days will be recorded using a Visual Analogue Scale

Illness beliefs and psychosocial determinants of health and behaviour will be recorded using the Illness Perception Questionnaire (IPQ), Geriatric Depression Scale (Short Form) (GDS-SF) and the Pain Self-Efficacy Questionnaire (PSEQ).

Qualitative Experience outcome

Analysis Methods

Feasibility and qualitative data analysis

Descriptive statistics will be used to characterize the groups at baseline and to present the feasibility outcomes.

Outcomes related to experience and perception via focus groups will be analysed by framework analysis.

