Recruitment target/Number recruited.					
Recruitment rate (n/centre/month)					
Outcome completion rate					
Reasons for withdrawal from intervention					
Retention rate (proportion of participants with valid primary outcome data at 3-months follow-up)					
Retention rate (proportion of participants with valid ActivPAL outcome data at 3-months follow-up)					
Reason for withdrawal from follow up					
Timing of withdrawal					
Intervention uptake and Adherence rate					
Attendance to PE					
Summary from phone calls					
TENS log summary					
Objective record of TENS use					
Acceptability of intervention					
Acceptability questionnaire					
Adverse events rate					
List them					
TENS blinding					

PrEPAID Statistical Analysis Plan (Version 1.0)
 Approval date:

Table 3: Changes in groups' outcomes at 6-wweks compared to placebo (usual care alone)

	TENS	PE+TENS	PE
ACD	$x \pm sd$ vs $x \pm sd$; $p=xxx(95\%cl)$		
ICD			
Daily steps			
Upright events			
Walking events			
EBCD			
ICQ			
SF-36			
7-day Average pain intensity			
Pain quality			
IPQ			
GDS-SF			
PSEQ			

*Also compare between PE+TENS and each of TENSs and PE alone (May not present in a table)

PrEPAID Statistical Analysis Plan (Version 1.0)
 Approval date:

Table 4: Changes in groups' outcomes at 3 months compared to placebo (usual care alone)

	TENS	PE+TENS	PE
ACD	$x \pm sd$ vs $x \pm sd$; $p=xxx(95\%cl)$		
ICD			
Daily steps			
Upright events			
Walking events			
EBCD			
ICQ			
SF-36			
7-day Average pain intensity			
Pain quality			
IPQ			
GDS-SF			
PSEQ			

*Also compare between PE+TENS and each of TENSs and PE alone ((May not present in a table)

Table 5: Within group comparisons between baseline and after 6 weeks intervention and 3 months follow up

	TENS	PE+TENS	PE	Usual care alone
ACD Post 6 wks Post 3 months follow up	$x \pm sd$ vs $x \pm sd$; $p = xxx$ (95%cl)			
ICD Post 6 wks Post 3 months follow up				
Daily steps Post 6 wks Post 3 months follow up				
Upright events Post 6 wks Post 3 months follow up				
Walking events Post 6 wks Post 3 months follow up				
EBCD Post 6 wks Post 3 months follow up				
ICQ Post 6 wks Post 3 months follow up				
SF-36 Post 6 wks Post 3 months follow up				
7-day mean pain intensity Post 6 wks Post 3 months follow up				
Pain quality				

PrEPAID Statistical Analysis Plan (Version 1.0)
Approval date:

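### ACD, the only primary efficacy outcome, has no primary time point and no single tested contrast: six unranked tests at 0.05 carry about a 20% false-positive chance, and the power figure belongs to no stated visit

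*SAP*

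**What the plan says.** **Outcome and timing.** Protocol 4.2.2 and SAP Section 6 both make ACD the primary outcome and list the other efficacy measures as secondary. On timing, SAP Section 6 says only: "Measurement will be obtained at baseline, following six weeks intervention and at 3 months follow up". Neither post-baseline time is called primary. The one place that ties the primary outcome to a time is a retention row in SAP Table 2, which uses 3 months. The two documents also count those 3 months differently: SAP Section 3 from randomisation, protocol Visit 5 from the end of the intervention.

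**Contrast.** Protocol 8.7 states, "at 80% power and a two-tailed 5% significance level", that "16 participants per group will allow detection of an effect size of 1.0 standard deviations of ACD in active TENS group compared to placebo control". It then applies the same effect size to both pilot studies, giving 169 m for TENS and 322 m for SEDRIC. SAP Section 3 (Framework) plans superiority comparisons of PE+TENS, PE+Placebo TENS and TENS with Placebo TENS. It does not rank the three or single out ACD.

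**Error rate.** SAP Section 4: "Analysis will be conducted at 95% CI, and 0.05 level of significance". No adjustment or testing order is given. Tables 3 (6 weeks) and 4 (3 months) each have 13 outcome rows and three columns compared with placebo. The one template cell filled in, ACD for TENS, shows a p-value and a 95% CI.

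**Numbers.** Protocol 8.7: "We will recruit 20 participants in each group, allowing for 20% attrition, and therefore aim to recruit 80 patients". Protocol Visit 5: "All participants recruited within first eight months of recruitment will be invited to return for a 3-month follow-up visit". Protocol Section 4 calls these participants a sub-group.

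**The concern.** The 5% error rate and the 80% power in 8.7 describe one test. A reader of the SAP cannot tell which cell of Tables 3 and 4 that test is: TENS alone or both TENS arms, at 6 weeks or at 3 months. With several candidate ACD results and no order among them, whichever falls below 0.05 could be put forward as the signal for a definitive trial. The synopsis rationale counts evidence of improvement in patient outcomes among the main considerations in that decision.

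The 3-month results raise a second problem. They share a table layout and a significance level with the 6-week results but come from fewer people, so a reader could carry the 8.7 power figure over to a visit for which it was not calculated.

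**Working it through.** **1. The plan's own figure.** Inputs from protocol 8.7: two-sided 5%, 80% power, difference 1.0 SD. By the normal approximation, n per group = 2 × (1.960 + 0.842)² / 1.0² = 15.7, rounded up to 16. Power at 16 = Φ(√(16/2) − 1.960) = Φ(0.868) = 0.807. For attrition, 16 / 0.80 = 20 per group, and 4 × 20 = 80. All three figures reproduce. A t-test gives 78% at 16 per group; the normal approximation is kept below so that any fall in power comes from n alone.

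**2. ACD tests.** 3 contrasts × 2 time points = 6. If independent, the chance of at least one false positive is 1 − 0.95⁶ = 0.265. They are not independent, because they share a placebo arm and the same patients at both times. Simulated with 16 per arm at both visits and an assumed between-time correlation of 0.3 to 0.7, the chance is about 0.20 to 0.24. At an assumed 0.8 it is 0.19. One named contrast at one time would give 0.05.

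**3. All comparisons in Tables 3 and 4.** 13 × 3 × 2 = 78. Expected number below 0.05 if no effect exists: 78 × 0.05 = 3.9, whatever the correlation. The chance of at least one does depend on correlation, which the documents do not give:

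| Assumed correlation between outcomes | Chance of at least one |
|---|---|
| 0 | 0.95 to 0.97 |
| 0.3 | 0.92 to 0.94 |
| 0.5 | 0.83 to 0.88 |
| 0.7 | 0.71 to 0.77 |
| 0.9 | 0.48 to 0.53 |

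The footnotes add PE+TENS against each single component (13 × 2 × 2 = 52), and Table 5 adds 13 × 4 × 2 = 104 within-group comparisons. Neither is in the 78.

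**4. Power at 3 months, single-arm contrasts.** Let R be the recruitment period in months (not stated, so assumed), with even accrual and attrition d. Then n per arm = 20 × (8/R) × (1 − d) for R of 8 or more, and power = Φ(√(n/2) − 1.960). At d = 20%:

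| R | n per arm | Power at 1.0 SD |
|---|---|---|
| 8 | 16.0 | 81% |
| 10 | 12.8 | 72% |
| 12 | 10.7 | 64% |
| 14 | 9.1 | 57% |
| 16 | 8.0 | 52% |

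Keeping 16 per arm requires R ≤ 20 × 8 × (1 − d)/16 = 10 × (1 − d). That is 8.0 months at 20% attrition, 9.0 and 9.3 at the pilot rates of 10% and 7.1%, and 10.0 with none. (Exactly 80% needs 15.7 per arm, so at 20% attrition power crosses 80% at 128/15.7 = 8.15 months.)

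**5. If TENS is pooled over education.** There are 40 recruits a side, so 16 a side lasts until R = 20 × (1 − d), or 16 months at 20% attrition. At 6 weeks there would be 32 a side, with power Φ(√(32/2) − 1.960) = 0.98 at 1.0 SD. The two readings of the contrast therefore have very different power.

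**The case against.** The strongest reply is that this is a feasibility trial. Protocol 8.1 and SAP Section 4 (Analysis populations) say that comparisons serve to estimate effect sizes with 95% CIs and that clinical differences are not the primary purpose. The only numeric rules for changing the definitive trial are the 10% eligibility and consent thresholds in protocol 8.2; no decision depends on a p-value. This stands, and it limits the seriousness of the point. It does not remove it, because the SAP still plans superiority comparisons at 0.05 and the synopsis lists ACD as a primary endpoint. The SAP's statement that no formal tests are pre-specified follows the feasibility, acceptability and adverse-event data and does not reach efficacy.

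A reader might also infer stronger things that the documents do not support:

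- **That all 13 outcomes rank equally.** They do not. ACD is labelled primary and the rest secondary, with separate analysis sections. Only the contrasts and times are unranked, so the ACD figure matters more than the figure for all 78.
- **That no contrast is named at all.** Section 8.7 names active TENS against placebo. The fault is that it can be read two ways and is not carried into the SAP.
- **That a chance finding is near certain.** That needs nearly independent outcomes; at a correlation of 0.9 the chance is about one half.
- **That the power claim fails unless recruitment ends within eight months.** That limit applies only to single-arm contrasts at the full 20% attrition, and it ignores any gain from the planned analysis of covariance. Nor does any text attach the 8.7 power to 3 months.

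Finally, 78 counts comparisons laid out in the table shells. Only one template cell actually shows a p-value.

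**Conclusion.** The point holds in a limited form and should be corrected before analysis. The plan has a primary efficacy outcome but not a primary test: its time point is missing and its contrast is ambiguous. For ACD, this raises the chance of at least one false positive from 5% to about 20%, on assumed between-time correlations. The expected 3.9 chance results among the 78 comparisons needs no correlation assumption, only that no effect exists and every cell is tested at 0.05.

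The loss of power at 3 months is conditional. Calling the 3-month set a sub-group suggests that recruitment was expected to run past month 8, but its length is not given. The size of the loss rests on that length, even accrual, the attrition rate, and whether TENS is compared by single arm or pooled.

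**What to change.** - **SAP Section 6:** name ACD at 6 weeks as the primary efficacy time point. It is the only post-baseline outcome assessment planned for every participant.
- **Same section, and the Framework in Section 3:** name one active v placebo TENS contrast as the only comparison tested at 0.05, and state whether it is the TENS-only arm against the Placebo TENS arm or both TENS arms against both placebo arms.
- **Tables 3 and 4:** label every other cell exploratory and lead with the estimate and 95% CI. P-values need not be deleted if they carry that label.
- **Protocol 8.7:** state that the power figure applies to that contrast at 6 weeks only. If the pooled contrast is chosen, restate the numbers per side.
- Reconcile the two definitions of the 3-month visit.

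The cost is wording and table-shell edits, with no new data or visits. The other comparisons lose any confirmatory standing, which fits the documents' own statement that clinical differences are not the primary purpose.

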Protocol deviation will be defined as accidental or unintentional changes to, or non-compliance with the research protocol that does not increase risk or decrease benefit or; does not have a significant effect on the subject's rights, safety or welfare; and/or on the integrity of the data. We will document deviations due to rescheduled study (If they fall outside the specified window), failure to complete a physical activity outcome assessment or self-report questionnaire, patients' refusal to complete scheduled research activities. Details regarding level (major or minor) number and type of protocol deviations per group will be summarised in addition to potential impact on analysis populations.

Analysis populations

Comparisons will be undertaken to investigate the feasibility of studying the proposed outcomes for definitive trial and to calculate estimates for the likely effect sizes and 95% confidence intervals, even though determining differences in clinical outcomes is not the primary purpose of this feasibility trial. Inferential analysis will be implemented using the principles of intention-to-treat.

SECTION 5: STUDY POPULATION

Screening, Eligibility and Recruitment Data:

The number of potential participants screened, eligible and the number recruited will be analysed and presented in a CONSORT flow diagram. Data regarding level of withdrawal from intervention and/or follow up as well as timing of withdrawal/lost to follow up will be analysed. In addition, data descriptive of reasons and details patterns of withdrawal/lost to follow up will be presented.

Baseline patient characteristics

The following patient baseline characteristics will be summarised: Age, gender, ABPI score, Diagnosis of APD, Diagnosis of IC, Past medical history, Cardiac risk factors, Present drug history. Also selected outcome measures including, ICD, ACD, McGill and VAS pain scores, SF-36 and ICQ OoL scores, Geriatric depression questionnaire, Pain self-efficacy questionnaire, and Brief illness perception questionnaire scores will be presented as baseline characteristics. Categorical data will be presented using counts and percentages. Continuous data will be presented using number of patients, mean (SD), median (min-max), and IQR.

SECTION 6: ANALYSIS

Outcome definitions

Feasibility and acceptability outcomes:

Measure recruitment rates -reasons for non-eligibility and non-recruitment of eligible patients will be recorded via the study screening log

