To determine the feasibility of conducting a definitive trial, descriptive statistics will be used to report the number and proportion of participants who meet the inclusion criteria, who consented to participating, and who dropped out during the trial. Also descriptive analysis will report compliance with intervention by recording participants' attendance to education session, follow up calls, attendance to TENS training session, (rate of use of TENS) rate of outcome measure completion, and total accelerometer wear time. Specifically, the TENS log (questionnaire) as well as inbuilt record of TENS device usage will both be used to analyse patients utilisation of TENS. Acceptability of TENS will be obtained by TENS feedback questionnaire

Further exploration will be carried out to determine factors that impact on propensity to participate looking at the difference in characteristics between participants and non-participants. If less than 10% of the individuals with PAD/IC in the clinic are eligible to participate, or if less than 10% of eligible patients agreed to participate, then the eligibility criteria and recruitment strategy will be adjusted prior to conducting a definitive trial. Adjustment of the recruitment strategy in a definitive trial will be made comparing the difference in the baseline characteristics between participants and non-participants. Similarly, association between participants' baseline characteristics and trial outcome will also inform decision on adjustment of recruitment strategy and stratification factors in the definitive trial. Data collection for the definitive trial will be adjusted based on the information related to type, quantity of missing data, and the mechanisms by which these data are missing.

The transcripts from the focus group discussions will be analysed using framework analysis. The data gathered from the exit interview will form part of acceptability analysis and be used to adapt the intervention to enhance its acceptability in a definitive trial.

Primary efficacy analysis

Differences in the change in ACD will be analysed and effect scores calculated using Chi-squared tests, Mann-Whitney U or Wilcoxon signed-rank tests as applicable for between and within-group comparisons and log-rank method for pooled samples or sub-strata. Baseline participants' variability will be controlled for using the analysis of co-variance.

Secondary efficacy analysis

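### The 3-month ACD comparison makes no use of the 6-week ACD of participants without a 3-month visit; one mixed model over both visits would recover some of that precision at little cost.

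*SAP*

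**What the plan says.** On principle, the SAP (Section 4, Analysis populations) says that "Inferential analysis will be implemented using the principles of intention-to-treat". Protocol 3.5 (Retention Rates) explains this as continuing to follow participants who do not use TENS or do not attend the education class. It adds that data gathered before a withdrawal will still be analysed.

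On method, the SAP (Section 6, Primary efficacy analysis) and Protocol 8.3 list for change in ACD chi-squared tests, "Mann-Whitney U or Wilcoxon signed-rank tests as applicable for between and within-group comparisons", the log-rank method for pooled samples or sub-strata, and ANCOVA to control for baseline. The secondary outcomes, including ICD, get the same list without ANCOVA. SAP Table 3 reports arms against placebo at 6 weeks and SAP Table 4 does so at 3 months.

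On who has a 3-month value, Protocol 4.1 (Visit 5) says: "All participants recruited within first eight months of recruitment will be invited to return for a 3-month follow-up visit". SAP Section 3 (Trial design) agrees. Neither document says what share of the 80 this will be.

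On missing outcomes, the only text (Protocol 8.2, repeated in SAP Section 6) concerns data collection in the later definitive trial. No repeated-measures model, imputation or missing-data rule is given for this trial's own comparisons.

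**The concern.** Mann-Whitney, Wilcoxon and ANCOVA applied at one visit can use only participants who have that visit's value. The log-rank method can accommodate a censored walking distance but not a treadmill test that never took place. Table 4 would therefore rest on early recruits who returned. Later recruits will have a baseline and a 6-week ACD. The 6-week value is likely to be informative about the 3-month one, yet the listed methods have no way to use it there.

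The comparisons exist to give effect sizes and confidence intervals for planning a definitive trial (Protocol 8.1; SAP Section 4). What is at stake is the precision of the 3-month estimates in arms of 20 or fewer. A second, conditional risk is bias, if participants who did poorly at 6 weeks are the ones who fail to return. The practice also sits awkwardly with the undertaking in Protocol 3.5 to analyse data already collected from those who withdraw.

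**Working it through.** **1. The plan's own figure.** Protocol 8.7 states "16 participants per group will allow detection of an effect size of 1.0 standard deviations of ACD" "at 80% power and a two-tailed 5% significance level". By the normal approximation, power = Φ(d√(n/2) − 1.96). With d = 1 and n = 16 this is Φ(2.83 − 1.96) = 0.807, so 16 reproduces. (The exact t-test gives 0.781 at 16 and needs 17.) Inflating, 16/0.8 = 20 per group, and 4 × 20 = 80, which matches "We will recruit 20 participants in each group, allowing for 20% attrition, and therefore aim to recruit 80 patients". The 20% is an allowance for attrition; pilot attrition was 7.1% to 10%. Nothing in it covers 3-month visits that are never scheduled.

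**2. Variance at 3 months.** Let n6 be the number per arm with 6-week ACD, n3 the number of those who also have 3-month ACD, and ρ the correlation between the two values given baseline. For this nested pattern,

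variance (likelihood model) / variance (3-month values only) = 1 − (1 − n3/n6) × ρ².

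The documents give neither n3/n6 nor ρ. I assume 0.5-0.8 for each:

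| n3/n6 | ρ | Ratio | Reduction |
|---|---|---|---|
| 0.5 | 0.5 | 1 − 0.5 × 0.25 = 0.875 | 12.5% |
| 0.5 | 0.8 | 1 − 0.5 × 0.64 = 0.680 | 32% |
| 0.8 | 0.5 | 1 − 0.2 × 0.25 = 0.950 | 5% |
| 0.8 | 0.8 | 1 − 0.2 × 0.64 = 0.872 | 12.8% |

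If n3 = n6 the ratio is 1 and nothing is gained.

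**3. What this means at the planned size.** Take n6 = 16 and a true difference of 1.0 SD, ignoring the baseline covariate. Effective n is n3 divided by the ratio, and power follows from the formula in step 1:

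| n3 per arm | Power, 3-month values only | Effective n, ρ = 0.5 / 0.7 | Power, mixed model, ρ = 0.5 / 0.7 |
|---|---|---|---|
| 8 | 0.52 | 9.1 / 10.6 | 0.57 / 0.63 |
| 10 | 0.61 | 11.0 / 12.3 | 0.65 / 0.70 |
| 12 | 0.69 | 12.8 / 13.7 | 0.72 / 0.74 |

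The formula is a large-sample result. Simulation of two arms at these sizes gave slightly smaller gains. At n3 = 8 the ratios were 0.906 (ρ = 0.5) and 0.779 (ρ = 0.7), against 0.875 and 0.755 from the formula.

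**4. Bias.** When the 3-month value is absent by design, the simulated estimate from 3-month values alone averaged 1.00 for a true 1.00. As an illustration of selective loss, I let active-arm participants with poor 6-week results be the ones lost (n3 = 8-12, ρ = 0.5-0.85). The estimate from 3-month values alone then averaged 1.14-1.50, against 0.99-1.01 for the likelihood estimate. In that scenario the precision gain shrank, and it vanished at n3 = 8, ρ = 0.5 (ratio 1.04).

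**The case against.** Several stronger conclusions are tempting, and the documents do not support them.

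- **That the tests contradict intention to treat.** They do not. Protocol 3.5 uses the term for following up non-adherers, and comparing participants by allocated arm with a rank test or ANCOVA fits that. The mixed model also omits anyone with no post-baseline value. What remains is the tension with the promise, in the same section, to analyse data already collected.
- **That 6-week data are thrown away.** Every 6-week value is used in Table 3. It is only not borrowed for Table 4.
- **That Table 4 will be biased.** Recruitment date is fixed before allocation and applies equally to all arms, so absence for that reason costs precision only. For ACD, ANCOVA already handles loss that depends on baseline ACD and arm. The bias this model could remove needs loss after week 6 to depend on 6-week ACD beyond those two. The 1.14-1.50 above is a constructed case, not a forecast.
- **That the gain can be read from the share of all 80 participants with 3-month data.** The formula needs the share among those with 6-week data. If 20% were lost by week 6 (an assumption), 50-80% of all participants would become n3/n6 = 0.5/0.8 to 0.8/0.8 = 0.625-1.0. The reduction would then be 0.375 × 0.25 to 0.375 × 0.64, or 9-24%, at the low end and zero at the high end.

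It is also fair to say that this is a feasibility trial, that detecting clinical differences is expressly not its main purpose, and that the SAP does not exclude imputation. These limit the weight of the point. They do not change the fact that the methods actually listed are less precise at 3 months than one the trial could run on the same data.

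**Conclusion.** The point holds as an efficiency improvement to the 3-month comparison. Under the listed visit-by-visit methods, the 6-week ACD of later recruits and of those lost between visits adds nothing to Table 4. A joint model would lower the variance of the 3-month effect by about 5-32% if n3/n6 and ρ both lie between 0.5 and 0.8. Both ranges are assumptions. The gain is zero if n3 = n6, small at 6 weeks in any case, and somewhat below the formula at these sample sizes. Protection against bias is a secondary benefit, conditional on loss related to 6-week ACD and on data being missing at random. No confirmatory conclusion is at risk. What improves is the estimates that will inform the definitive trial.

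**What to change.** Amend SAP Section 6 so that, for ACD and ICD, between-arm effects at both visits come from one linear mixed model:

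- outcomes: the 6-week and 3-month values;
- fixed effects: arm by visit, baseline value by visit, and the stratification factors (gender, age, ABPI);
- unstructured covariance for the two visits, with Kenward-Roger degrees of freedom;
- population: all randomised participants with any post-baseline value, analysed as allocated.

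Fix the analysis scale (metres or log) before unblinding, not after inspecting results by arm; the log scale gives ratios, whereas Protocol 8.7 plans in SDs and metres. State the missing-at-random assumption, and report n6 and n3 by arm beside Table 4. Keep the rank tests as sensitivity analyses.

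The cost is SAP wording and standard code, with no new data or visits. The SAP leaves SAS or SPSS open, so name one and confirm that it offers the chosen degrees-of-freedom method. The downsides are reliance on approximate normality, which the planned ANCOVA for ACD already implies but which is new for ICD, and reliance on missing at random. Participants with no post-baseline value still contribute nothing.
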